Clarification and update to the list of AESIs and the respective definition the AE table section, including analysis by type of surgery (spinal and a surgery) 12.6.3 Laboratory Data. Analysis by type of surgery (spinal and abdomine the section) 6.0	abdominal ninal surgery). 5.1 and
6.0 New exploratory efficacy endpoint "Overall Mortality" added to section 5	5.1 and
	escribed in
Update to section 8.6. New subgroups added. These subgroups are de more detail in section 12.	
Update to the definition of correction of fibrinogen level in section 8.12	
Definition of overall mortality added to section 8.19	
Update to section 9.3 describing the full analysis set to be in line with the guidelines. The previous full analysis set is now described in section 9.3	
Tabulation of prohibited medication added to section 12.3.2	
In section 12.5 new subgroups are added and the word ANCOVA is no with ANOVA,	w replaced
Section 12.5.1.3 and 12.5.1.4 describe checking of ANOVA assumption alternative strategies in case the assumptions are significantly violated.	
Section 12.5.3.1 updated to include Pearson's correlation between fibri and MCF Clauss assay.	inogen level
Plasma derived drugs removed from section 12.5.3.2 describing consu- transfusion products after IMP until end of surgery. Summary of subject avoidance of transfusion products post IMP administration added.	
Section 12.5.3.7. Method to produce the confidence internal added.	
Section 12.5.3.8 added to describe the analysis of overall mortality.	
Section 12.6.1 updated to accommodate new adverse event analyses a analyses.	and subgroup
In section 12.6.3 a shift summary of hematology for number of subjects from normal or not clinical significant to clinical significant has been add	

Table of Contents

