7.2 Secondary Parameters

7.2.1 Efficacy

Secondary efficacy will be determined using the following parameters:

- Proportion (%) of subjects with successful correction of fibrinogen level (FIBTEM A10) 15 minutes after start of first IMP administration.
 Successful correction of fibrinogen level in a subject is defined as restoring fibrinogen FIBTEM A10 baseline level to at least 95% measured by ROTEM 15 minutes after start of first IMP administration. A correction of at least 95% is considered successful, as measurement methods has a coefficient of variation of about 5% (Solomon et al., 2015).
- Time to first successful correction of fibrinogen level (15 minutes or 90 minutes after start of first IMP administration, end of surgery, not within surgery).
- Total amount (volume in mL and number of units [bags]) of transfusion products (allogeneic blood products) or autologous blood transfusion infused after start of first IMP administration until end of surgery. The end of surgery is defined as time of last suture.
- Amount (volume in mL and number of units [bags]) of red blood cells (RBCs) (allogeneic and autologous) infused after start of first IMP administration until end of surgery. The end of surgery is defined as time of last suture.

- Post-operative blood loss in the first 24 hours.
- Proportion (%) of subjects with rebleeds after the end of surgery until Day 8. Rebleeds are defined as any bleed requiring hemostatic treatment (including reoperation) after the end of surgery until Day 8.
- Hospital length of stay after surgery, defined as the date of discharge minus the date of surgery.
- In-hospital mortality.

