8.12 Correction of Fibrinogen Level

The fibrinogen level is assessed by FIBTEM A10 test, MCF and Clauss assay at the following visits: screening, prior surgery (baseline), Surgery Day 1 (Prior 1st dose), Surgery Day 1 (Predose)*, Surgery Day 1 (15 minutes after start of first IMP administration), Surgery Day 1 (90 minutes after start of first IMP administration), Surgery Day 1 (end of surgery), and Day 2, Follow-up Visit. (* only applicable in case of repeated intra-operative IMP administration).

Rate of fibrinogen restoring = fibrinogen level at a post-baseline visit / fibrinogen level at baseline*100

If the rate of fibrinogen restoring is \geq 95%, then the fibrinogen level is considered to be successfully corrected at that post-baseline visit for the subject.

The above rate will be calculated for the following visits: Surgery Day 1 (15 minutes after start of first IMP administration), Surgery Day 1 (90 minutes after start of first IMP administration), Surgery Day 1 (End of surgery), and Day 2, Follow-up.

The time to first successful correction of fibrinogen level is classified into the following categories: "Within 15 minutes after IMP start", "Greater than 15 and less than or equal to 90 minutes after IMP start", "Greater than 90 minutes after IMP start" and "Unsuccessful correction".

At every visit, the time point relative to the start time of IMP is calculated in minutes as Collection Time of sample minus Start Time of IMP. Any corrections <15 minutes after IMP start are not considered for classification.

The earliest time point, when the rate is \ge 95%, is the time to first successful correction of fibrinogen level and will be used to categorize the subjects into the respective categories.

Subjects with time to first successful fibrinogen correction on Follow-up Visit Day 2 will be assigned to the category "Greater than 90 minutes after IMP start". If the rate of fibrinogen restoring is < 95% at all the time points, correction of fibrinogen level is reported as "Unsuccessful correction".

A sensitivity analysis adds a time window of ±3 minutes to the category "Within 15 minutes after IMP start", so that time points ≥12 and ≤18 minutes fall into this category. To the category "Greater than 15 and less

than or equal to 90 minutes after IMP start" a time window of +3 minutes is added, so that time points between >18 and ≤93 minutes fall into this category. Corrections >93 minutes are categorized as "Greater than 90 minutes after IMP start".

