In addition, and independent from the above categories, the time to first successful correction is classified into "Until end of surgery" or "Not within surgery". Subjects with time to first successful correction at the time point Surgery Day 1 (End of surgery) are assigned to "Until end of surgery". Subjects with time to first successful correction on Follow-up Visit Day 2 are assigned to "Not within surgery". For the visits Surgery Day 1 (15 minutes after start of first IMP administration) and Surgery Day 1 (90 minutes after start of first IMP administration) and Surgery and subjects are assigned to "Until end of surgery" or "Not within surgery" accordingly. If the rate of fibrinogen restoring is < 95% at all the time points, correction of fibrinogen level is reported as "Unsuccessful correction".

The whole analysis for the correction of fibrinogen levels is also done based on results obtained from MCF and Clauss assay to perform sensitivity analyses.

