12.5.3.1 Correction of Fibrinogen Level

The proportion (%) of subjects with a successful correction of fibrinogen level (by FIBTEM A10) 15 minutes after start of first IMP administration will be compared between the treatment arms using a Cochran-Mantel-Haenszel (CMH) approach stratified by predictive blood loss (> 1,000 mL to \leq 2,000 mL and > 2,000 mL). The number and percentage of subjects with a successful correction of fibrinogen level 15 minutes after start of first IMP administration will be presented for both treatment arms with corresponding 95% confidence intervals. The estimated treatment effect (i.e., the difference in response rate between the treatment arms, BT524 – FFP/cryoprecipitate), corresponding 95% confidence interval, and 2-sided p-value for the difference will be presented.

The time to first successful correction of fibrinogen level (by FIBTEM A10) is assigned to the following categories: "Within 15 minutes after IMP start", "Greater than 15 and less than or equal to 90 minutes after IMP start", "Greater than 90 minutes after IMP start" and "Unsuccessful correction". The 4 categories will be compared between the two treatment arms using a Chi-square test.

In an additional analysis the time to first successful correction of fibrinogen level (by FIBTEM A10) is classified relative to the end of surgery into "Until end of surgery", "Not within surgery" or "Unsuccessful correction". The 3 categories will be compared between the two treatment arms using a Chi-square test.

For the above Chi-square tests, the number and percentage of subjects in each category will be presented for each treatment arm, together with an overall p-value for the difference between the two treatment arms.

The absolute values and change from baseline in fibrinogen levels by FIBTEM A10, together with the rate of fibrinogen restoring will be summarized with descriptive statistics over time by treatment arm. The absolute values at screening and change from screening at baseline will also be summarized for fibrinogen levels by FIBTEM A10.

In addition, the test results of MCF and Clauss assay will be summarized in the same way. The results of these three assays will be listed for the All Subjects Enrolled Set.

Mean with SD, median with interquartile ranges will be presented graphically over time for both treatment arms for FIBTEM A10, MCF and Clauss assay.

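### As written in SAP 8.12, the first category of time to fibrinogen correction can hold only a sample drawn at exactly 15 minutes

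*SAP*

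**What the plan says.** SAP 7.2.1 lists the secondary endpoint as "Time to first successful correction of fibrinogen level (15 minutes or 90 minutes after start of first IMP administration, end of surgery" and, as its last level, not within surgery. These are scheduled time points. Protocol 9.1.2.2 defines the endpoint in the same way, and protocol 10.6.1 counts the subjects corrected at each scheduled time point.

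SAP 8.12 works differently. It takes elapsed time as sample collection time minus IMP start time, finds the earliest time at which FIBTEM A10 is at least 95% of baseline, and assigns the subject to one of four categories: within 15 minutes; above 15 and up to 90 minutes; above 90 minutes; or unsuccessful. It adds: "Any corrections <15 minutes after IMP start are not considered for classification". The unsuccessful category is worded conditionally: "If the rate of fibrinogen restoring is < 95% at all the time points".

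A sensitivity analysis widens the first category, "so that time points ≥12 and ≤18 minutes fall into this category", and lets the second run from above 18 to 93 minutes.

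SAP 12.5.3.1 tests the main classification: "The 4 categories will be compared between the two treatment arms using a Chi-square test". There is also a separate classification relative to surgery, introduced with "In addition, and independent from the above categories, the time to first successful correction is classified into". The rules are repeated for two other assays: "The whole analysis for the correction of fibrinogen levels is also done based on results obtained from MCF and Clauss assay".

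The SAP change history records "Update to the definition of correction of fibrinogen level in section 8.12" without saying what changed. SAP 4.1, which lists changes from the protocol, does not mention this endpoint.

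**The concern.** The category label promises every correction seen by 15 minutes. The exclusion removes everything earlier than 15 minutes, and the next category takes everything later, so one minute value is left. Samples are scheduled at 15 minutes, but the main rule gives no tolerance around that time.

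Three things are at stake in this table:

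- Correctly timed samples taken a minute early or late are moved to a later category or ignored.
- A subject whose only corrected sample was drawn before 15 minutes has no clear category. Read literally, the unsuccessful category does not apply, because the rate was not below 95% at every time point. If the ignored sample is treated as absent, the subject is reported as unsuccessful. Both readings misstate a subject who was corrected, and the programmer has to choose.
- The proportion corrected at 15 minutes is based on the visit, so it counts all these samples. Two tables in the same report can then disagree about the same blood draw.

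The early category is also the informative one. The protocol describes a BT524 syringe as taking less than 20 seconds (section 3) and two cryoprecipitate pools as taking about 30 minutes (section 6.2).

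**Working it through.** The plan gives no figure to reproduce here. The first two steps are logic from the text. The third is illustrative.

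**Step 1. The admissible set.** Let t be elapsed minutes. The first category needs t ≤ 15. The exclusion removes t < 15. What remains is t ≤ 15 and t ≥ 15, so t = 15.

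**Step 2. Every whole minute from 0 to 120 under both rules.**

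| Outcome for a corrected sample | Main rule | Sensitivity rule |
|---|---|---|
| Not considered / no category stated | 0–14 | 0–11 |
| First category | 15 only | 12–18 |
| Second category | 16–90 | 19–93 |
| Third category | 91 and later | 94 and later |

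The first category holds one whole-minute value under the main rule and seven under the sensitivity rule. The sensitivity rule does not say where a correction before 12 minutes goes.

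**Step 3. How many samples this could affect.** The documents do not give the scatter of draw times, so it is assumed: true draw time is Normal around the scheduled time with standard deviation s, recorded to the nearest minute. With Φ the standard normal distribution function:

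- P(t < 15) = Φ(−0.5/s), and by symmetry P(t > 15) is the same. For the 90-minute draw, P(t > 90) is also the same.
- P(t = 15) = 2Φ(0.5/s) − 1
- P(12 ≤ t ≤ 18) = 2Φ(3.5/s) − 1
- P(t ≤ 18) = Φ(3.5/s)
- For the 90-minute draw, P(t > 93) = 1 − Φ(3.5/s)

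| Quantity | s = 1 | s = 2 | s = 3 |
|---|---|---|---|
| 15-min draw ignored (t < 15) | 0.309 | 0.401 | 0.434 |
| 15-min draw in first category (t = 15) | 0.383 | 0.197 | 0.132 |
| 15-min draw in second category (t > 15) | 0.309 | 0.401 | 0.434 |
| 90-min draw pushed past 90 | 0.309 | 0.401 | 0.434 |
| 15-min draw within 12–18 | 0.9995 | 0.920 | 0.757 |
| 15-min draw at or before 18 | 0.9998 | 0.960 | 0.878 |
| 90-min draw pushed past 93 | 0.0002 | 0.040 | 0.122 |

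**Step 4. In subjects.** Suppose 60 of 100 subjects are corrected at the 15-minute visit (also an assumption). The visit-based proportion shows 60. The first category of the timed table shows 60 × 0.383 = 23.0, 60 × 0.197 = 11.8 or 60 × 0.132 = 7.9. Counting every draw up to 18 minutes gives 60 × 0.9998 = 60.0, 60 × 0.960 = 57.6 or 60 × 0.878 = 52.7.

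**The case against.** The strongest reply is that the SAP already eases the problem. It prespecifies the tolerant windows as a sensitivity analysis. It reports the visit-based 15-minute proportion separately. It also adds the classification relative to surgery. The same cut-offs apply to both arms, SAP 12.5.2 calls the secondary analyses exploratory, and the schedule asks for draws at 15 and 90 minutes, so recorded times may cluster on those values.

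Part of this stands. The primary result is not touched, no direction of bias follows, and clustering on the nominal times would shrink the effect. The shares above also count samples, not subjects. A subject whose early sample is ignored is still classified if a later sample is corrected, and how often none is cannot be estimated from the documents.

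The rest does not rescue the main table. The sensitivity analysis leaves the main rule as it is and has its own gap below 12 minutes. The surgery split does not restore the 15- and 90-minute levels. Choosing a ±3 minute window shows that off-time draws were foreseen.

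Two objections to the remedy are fair and need an open answer. The SAP's window has a floor of 12 minutes, so removing it is a new rule. With the floor kept, the first category would hold 92% (s = 2) or 76% (s = 3) of 15-minute draws, not 96% or 88%. Without a floor, a very early draw counts as a correction within 15 minutes. That agrees with the category's label, but the SAP should say so.

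**Conclusion.** The concern holds as stated. That the first category admits only t = 15 follows from the wording of SAP 8.12 and rests on no assumption. The conflict with SAP 7.2.1 and with protocol 9.1.2.2 and 10.6.1 is equally plain, and SAP 4.1 does not disclose it.

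The size is uncertain. Under the assumed SDs of 1 to 3 minutes, between 38% and 13% of corrected 15-minute samples would qualify as such, and between 31% and 43% of corrected 90-minute samples would be labelled later than 90 minutes. These are illustrations, not forecasts.

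The reach is limited to the four-category table, its Chi-square test, and the repeats by assay and type of surgery. It should be corrected before database lock, because the change is small and the table would otherwise misreport corrected subjects.

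**What to change.** Delete the exclusion of corrections before 15 minutes from the main rule in SAP 8.12. Then choose one of two main rules:

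- **(a) Scheduled visit.** Classify by 15 minutes, 90 minutes, end of surgery or Day 2, using the earliest corrected sample in time, with a separate unsuccessful category. This stays closest to SAP 7.2.1 and the protocol, but it gives five levels where the protocol has four.
- **(b) Elapsed time.** Use the SAP's own upper limits: up to 18 minutes, above 18 to 93, above 93, and unsuccessful. State that every earlier draw belongs to the first category.

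Keep the other version as the sensitivity analysis, also with draws before 12 minutes in the first category. Under either option, leave surgery status to the separate classification already in SAP 8.12. A 90-minute draw taken after the end of surgery, which protocol 7.1 allows, then has one label on each axis. Keep the Chi-square test.

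Align SAP 7.2.1, 8.12 and 12.5.3.1, and list the remaining departure from the protocol in SAP 4.1. The cost is a few sentences, a revised table shell and one line in SAP 4.1. No new data and no protocol change are needed.

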8.13 Amount of Transfusion Products

All types of transfusion products administered, including RBCs will be counted. The volumes and units (bags) of all these products will be summarized by type of transfusion product, and by treatment arm.

8.14 Amount of Red Blood Cells

The volumes and units (bags) of allogeneic RBCs and autologous blood transfusion/cell salvage will be counted separately.

8.15 Post-operative Blood Loss in the First 24 hours

The plasma drainage tube and disposable drainage bag will be emptied 24 hours after the end of surgery. The post-operative drainage volume in the first 24 hours is collected in eCRF.

8.16 Rebleeds after the End of Surgery until Day 8

Rebleeds are defined as any bleed requiring hemostatic treatment (including reoperation) after the end of surgery until Day 8, which are recorded in eCRF.

8.17 Hospital Length of Stay after Surgery

Length of stay after surgery (days) = date of discharge – date of surgery

Where date of discharge is the date of discharge following the IMP treated surgery.

8.18 In-hospital Mortality

In-hospital mortality is defined as death occurring during the hospital stay.

8.19 Overall Mortality

Overall mortality is defined as death occurring during study duration.

8.20 Relative Day

If the assessment date is prior to the date of IMP administration, the relative day is date of assessment minus date of IMP administration. If the assessment date is on the date of IMP administration or after that, then the relative day is the date of assessment minus date of IMP administration plus 1.

8.21 Time to Start of First Investigational Medicinal Product Infusion

Time to start of first IMP infusion = Start time of first IMP administration - Time of decision to treat subject with IMP.

8.22 Total planned Investigational Medicinal Product Volume Total planned IMP volume = Sum of all planned IMP volume.

8.23 Total actual Investigational Medicinal Product Administered Total actual IMP administered = Sum of all actual IMP administered.

8.24 Duration of Investigational Medicinal Product Infusion

Duration of XXX IMP administration = End time of XXX IMP administration - Start time of XXX IMP administration

Where XXX is the first, second ... administration.

8.25 Relative Time in Surgery

Duration of Surgery = End time of surgery - Start time of surgery

Time until decision to treat = Time of decision to treat subject with IMP - Start time of surgery

Time to end of surgery after decision to treat = End time of surgery - Time of decision to treat subject with IMP

Time of IMP exposure during surgery = End time of surgery - Time of start of first IMP administration

9.0 Analysis Sets

9.1 All Subjects Enrolled Set

The All Subjects Enrolled Set includes all subjects who have given informed consent to this study.

9.2 Safety Analysis Set

The Safety Analysis Set (SAF) comprises all subjects who have received at least one dose of IMP. Subjects will be analyzed according to the treatment received.

9.3 Full Analysis Set

All randomized subjects receiving IMP post randomization and with data collected post randomization will be included in the FAS. Exclusion from the FAS can be considered in special cases as described in ICH E9, section 5.2.1. For the purpose of this trial, there are two FAS: FAS and mFAS. All subjects will by default be included and analyzed according to the randomized treatment allocation in both definitions.

The decision to exclude subjects from FAS will be done at a data review meeting after reviewing the data as described in the Data Review Meeting Plan.

9.3.1 Modified Full Analysis Set

As per the section above, all randomized subjects will be included in the modified full analysis set (mFAS) who meet the following conditions.

- 1. Subjects who received at least one dose of IMP prior to the 'end of surgery' and
- 2. have at least one post-dose efficacy assessment.
- 3. This includes all subjects whose IMP infusion started prior to the end of surgery, irrespective of the amount of IMP infused.

Subjects will be analyzed as randomized. The decision to exclude subjects from mFAS will be done at a data review meeting after reviewing the data as described in the Data Review Meeting Plan.

9.4 Per-Protocol Set

The Per-Protocol Set (PPS) is a subset of FAS and includes all subjects who are compliant with the CSP without any major PDs thought to have the potential to impact the results of the efficacy analysis, e.g., no treatment with IMP, incomplete treatment with IMP (administration of the 1st IMP dose is not completed if the end of the 1st IMP administration is after the end of surgery), treatment with IMP after the 'end of surgery', no post-dose efficacy assessment for the primary endpoint. Classification of PDs as major or minor will be agreed upon at the BDRM prior to database lock and also prior to each Interim Analysis for eligible subjects.

Subjects will be analyzed according to the treatment received.

10.0 Interim Analyses and Data Monitoring

To ensure subject safety, the safety data will be evaluated by a DSMB at regular intervals. A DSMB charter and list of required tables and listings is available (see Appendix 1).

After 40 subjects have completed the study, a blinded sample size recalculation will be performed. See section 6.2.1 for details. A specification of required table and listing is available (see Appendix 1).

In this study, three interim analyses of the observed blood losses are planned to have the option of adjusting the sample size needed.

For this purpose, an alpha-adjustment according to Haybittle/Peto (Haybittle, 1971; Peto et al., 1976; Schulz and Grimes, 2005) is planned. This leads to local alpha levels of 0.001 for each interim analysis and a significance level of 0.05 for the final analysis to reach a global significance level of 5%.

Past interim analyses were based on the PPS, and past sensitivity analyses were based on the mFAS.

The first interim analysis is planned with approximately 50 spine subjects, the second one with at least 40 cytoreductive PMP subjects and all other evaluable spine subjects at that time point. The third interim analysis is planned after approximately 80% of subjects of the total sample size.

Aim of all interim analyses is to adapt the sample size according to the observed blood losses and the SDs:

- a) Early termination due to non-inferiority of BT524 in comparison with the used standard therapies.
- b) Continuation with the sample size as initially planned.
- c) Adjustment of sample size to take into account changes from the previous assumptions on the additional blood loss.
- d) Stopping the study early due to futility if the sample size re-estimation indicates a much higher number than planned before.

As soon as the approximate required number of subjects for an interim analysis has received at least one dose of IMP prior to the end of surgery, completed treatment, the relevant data points (including measurement and documentation of blood loss between decision to treat and end of surgery) have been satisfactorily reviewed and the corresponding items/forms have been frozen, a data snapshot will be taken. Further details are specified in the Planned Data Deliverables section of the Data Management Plan. Classification of PDs as major or minor will be agreed PD review meeting and then reviewed during the BDRM meeting based on the snapshot data.

At each interim analysis, the tables and listings which are specified in the document: Biotest 995 TFL Specifications for Interim Analysis of Sample Size (see Appendix 1) will be produced.

For the interim analysis, the sample size will be recalculated according to the observed blood losses and the SDs using nQuery Advisor version 4.0 or higher.

The interim analysis will be based on unblinded data. The analysis will be performed by an Independent Interim Analysis Team. The interim analysis outputs will be created in a secure, restricted-access storage area on the PPD SAS file-server. All derived datasets, analysis outputs, email communications, etc. created as part of an interim analysis and containing the potential to unblind or result in operational bias, must be handled in a manner such that the Project Team has no access to them. The Independent Reporting Statistician files the final datasets, and any email communication in a secure, restricted-access storage area.

The Independent Reporting Statistician shares only the newly calculated sample size and the recommendation (see rules above) from the interim analysis results with the Sponsor and PPD study team.

In the final BDRM meeting the need for additional subgroup definitions related to length between decision to treat and end of surgery will be evaluated. If required, additional subgroups will be added to the SAP and shells in a new SAP version prior to database lock and the final evaluation.

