## 10.8 Interim Analyses

In this study, 3 interim analyses of the observed blood losses are planned to have the option of adjusting the sample size needed (primary: PPS, secondary: FAS).

For this purpose, an alpha-adjustment according to Haybittle/Peto (Haybittle, 1971; Peto et al., 1976; Schulz and Grimes, 2005) is planned. This leads to local alpha levels of 0.001 for each interim analysis and a significance level of 0.05 for the final analysis to reach a global significance level of 5%.

All interim analyses will be based on the PPS.

The first interim analysis is planned with approximately 50 spine subjects, the second one with at least 40 PMP subjects and all other evaluable spine subjects at that time-point. The third interim analysis is planned after approximately 80% of subjects of the total sample size.

Aim of all interim analyses is to adapt the sample size according to the observed blood losses and the standard deviations:

- a.) Early termination due to non-inferiority of BT524 in comparison with the used standard therapies.
- b.) Continuation with the sample size as initially planned.
- c.) Adjustment of sample size to take into account changes from the previous assumptions on the additional blood loss.
- d.) Stopping the study early due to futility if the sample size re-estimation indicates a much higher number than planned before.

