12.0 Statistical Methods

All analyses will use SAS[®] version 9.4 or higher.

Subject data listings will be ordered by randomized or actual treatment ('Not randomized' / 'Not treated', 'BT524', 'FFP', 'Cryoprecipitate'), subject number (numerically, ascending) and visit of assessment respectively where applicable. All tables will be presented by treatment arm ('BT524', 'FFP/Cryoprecipitate') and overall. Where applicable tables will also be presented by treatment ('BT524', 'FFP', 'Cryoprecipitate') or by surgery (spinal, abdominal).

Unless otherwise noted, categorical variables will be summarized using number of observations (n), counts and percentages within category. Percentages will be rounded to one decimal place; except 100% will be displayed without any decimal places and percentages will not be displayed for zero counts.

Unless otherwise noted, continuous variables will be summarized using the number of observations (n), arithmetic mean, SD, minimum, Q1, median, Q3 and maximum. The minimum and maximum values will be displayed to the same level of precision as the raw data, the mean, median, Q1 and Q3 to a further decimal place and the SD to two additional decimal places. Unless stated otherwise the calculation of percentages will be based on the total number of subjects in the population of interest. Thus counts of missing observations will be included in the denominator and presented as a separate category.

The significance level will be 2.5% (one-sided), confidence intervals will be 95% (two-sided). All statistical tests (p-values) will be two-sided, unless otherwise stated.

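### Three interims at 0.001 with an unreduced final 0.05 slightly exceed the stated global 5%, and the final 95% interval makes no allowance if the observed difference changed N

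*SAP*

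**What the plan says.** SAP 10.0 names Haybittle/Peto as the adjustment and gives the levels: "This leads to local alpha levels of 0.001 for each interim analysis and a significance level of 0.05 for the final analysis". Protocol 10.8 says the same, with "a significance level of 0.05 for the final analysis to reach a global significance level of 5" per cent, and the synopsis repeats it. SAP 12.0 sets a one-sided 2.5% significance level and then adds "All statistical tests (p-values) will be two-sided, unless otherwise stated". The sidedness of 0.001 is not stated separately.

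The first option at each interim is "Early termination due to non-inferiority of BT524 in comparison with the used standard therapies". The last is "Stopping the study early due to futility if the sample size re-estimation indicates a much higher number than planned before". On re-estimation, SAP 10.0 says "The interim analysis will be based on unblinded data" and "the sample size will be recalculated according to the observed blood losses and the SDs using nQuery Advisor".

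SAP 12.5.1 declares non-inferiority if the upper limit of an ordinary 95% interval from the ANOVA lies below 150 mL. SAP 12.5.1.1 declares superiority at a two-sided p below 0.05. SAP 12.5.2 discusses type I error only for the step from non-inferiority to superiority. The SAP, dated June 2023, also records that "Past interim analyses were based on the PPS, and past sensitivity analyses were based on the mFAS".

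**The concern.** There are two separate issues.

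- **The looks.** An interim that can stop for success uses some of the type I error. If the final test still takes the full 0.05, the total must exceed 5%, whatever the timing.
- **The sample size.** Haybittle/Peto covers repeated looks at a fixed maximum N. It does not cover an N chosen from unblinded results. If the observed difference drives N, the ordinary pooled statistic no longer has its nominal distribution, and the 95% interval need not have 2.5% one-sided error. The independent interim team in SAP 10.0 limits operational bias but does not alter the test statistic. Neither document gives a combination test, a conditional-error rule, an adjusted interval or a cap on N.

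At stake is the primary claim of a pivotal non-inferiority trial at one-sided 2.5%.

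**Working it through.** **Inputs.** From SAP 10.0: three interims at 0.001 and a final at 0.05; first look at about 50 subjects; second with at least 40 PMP subjects plus all evaluable spine subjects; third at about 80%. From SAP 6.2: SD 375 mL, margin 150 mL, 100 evaluable per arm, 80% power, about 220 randomized. A true difference of 0 is assumed for power, because the documents do not state one.

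**Planned sample size.** n per arm = 2 × (1.960 + 0.842)² × 375² / 150² = 98.1, so 99 against the stated 100. Power of the t-test at 100 per arm is 80.4%. The planned N reproduces.

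**Global level at fixed N.** Information fractions are 50/200 = 0.25, t2, 0.80 and 1. The floor for t2 is (50 + 40)/200 = 0.45; above that its value is assumed. With corr(Zi, Zj) = √(ti/tj), overall alpha = 1 − P(|Z1|, |Z2|, |Z3| < 3.2905 and |Z4| < 1.9600), by multivariate-normal integration. The one-sided column uses the upper bounds only. The fourth column replaces 3.2905 with 3.0902, which is 0.001 one-sided.

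| t2 | Two-sided | One-sided | One-sided, if 0.001 is one-sided | Two-sided, final at 0.049 |
|---|---|---|---|---|
| 0.45 | 5.083% | 2.542% | 2.592% | 4.984% |
| 0.60 | 5.069% | 2.535% | 2.578% | 4.970% |
| 0.70 | 5.062% | 2.531% | 2.570% | 4.963% |
| 0.79 | 5.059% | 2.530% | 2.564% | 4.959% |
| Base 220 (0.227, 0.409, 0.80) | 5.091% | 2.546% | 2.600% | 4.992% |

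No timing returns 5.00%. Exactly 5% two-sided needs a final level of about 0.0492-0.0494 for t2 of 0.45-0.70. If 0.001 is one-sided, the final one-sided level must be about 0.0241-0.0243, that is 0.0481-0.0486 two-sided. In that case 0.049 is not quite enough.

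**Cost of 0.049.** SE = 375 × √(2/100) = 53.03 mL. Half-width = t × SE on 198 df: 1.9720 × 53.03 = 104.58 mL at 0.05, and 1.9808 × 53.03 = 105.05 mL at 0.049, a difference of about 0.5 mL. Noncentral-t power falls from 80.36% to 80.12%.

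**Re-estimation (illustrative).** The documents give no rule, so the following is assumed: true difference 150 mL, SD 375 mL, one homogeneous population, N reset for 80% power and never below 100 per arm, an ordinary final test at 0.05, and t2 of 0.5-0.7 unless noted. There were one million trials per cell (Monte Carlo SE 0.016 points). One-sided error:

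| Assumed rule | One-sided error |
|---|---|
| No re-estimation (t2 0.4-0.7) | 2.51-2.55% |
| SD only (true SD 375 or 450) | 2.57-2.61% |
| Observed difference, no futility stop, cap 1.5× | 2.81% |
| Same, cap 2× | 2.97-3.03% |
| Same, cap 3× | 3.16-3.25% |
| Observed difference, futility always obeyed at 1.5× to 10× (t2 0.4-0.7) | 0.62-1.65% |

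A separate normal-approximation run with total caps of 300-1000 gave 3.2-3.8% when N was also allowed to fall and futility was ignored. A fixed-weight inverse-normal combination of stage-wise tests, with N driven by the observed difference, gave 2.46-2.52% at a final level of 0.049.

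**The case against.** The excess from the looks alone rounds to the figures the documents print (5%, 2.5%), and an unreduced final level is the usual Haybittle/Peto convention. That is fair as to size. It does not make the stated level exact, and the correction is almost free.

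The two-sided reading of 0.001 is an inference. It fits the pairing with 0.05 and 5%. The one-sided reading makes the excess slightly larger, so the point does not depend on it.

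A reader might infer that the trial runs at about 3% one-sided error. The documents do not support that, for three reasons:

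- **Rule.** The larger figures need N to follow the observed difference and futility to be ignored. With the difference truly at the margin, effect-based re-estimation tends to ask for a very large N, which is the situation the futility option describes. If it is always obeyed, the error falls below 2.5%. That option has no threshold and is not called binding, however, so it cannot be relied on for control.
- **Input.** The sample-size adjustment option refers to assumptions about additional blood loss. Protocol 10.9 uses that term for the assumed 500 mL in the comparator arm, not for a treatment difference. This points away from an effect-driven rule without settling it. The separate interim specification listed in SAP Appendix 1 may say more.
- **Whether N changed.** The June 2023 SAP keeps 100 evaluable per arm and about 220 randomized. It records the effect of the earlier blinded recalculation in SAP 6.2 and 6.2.1, but no later change. This suggests that N stayed as planned, though the SAP does not say so.

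**Conclusion.** The point holds on both parts, with different weight.

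The stated global 5% is not attained. At fixed N the excess is 0.06-0.09 percentage points two-sided, or 0.06-0.10 points one-sided if 0.001 is one-sided. This assumes that information is proportional to subject count; unequal variances in spine and PMP subjects would shift the figures slightly.

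For re-estimation, control is undemonstrated rather than shown to be lost. The documents fix neither the size nor the direction of any departure. If N was never changed, or only the SD was used, little remains beyond the small excess from the looks. If N was changed on the observed difference, the ordinary 95% interval has no demonstrated 2.5% error. This should be settled before database lock.

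**What to change.** 1. **Final level.** Use a two-sided 0.049 with a 95.1% interval for non-inferiority in SAP 12.5.1, and p < 0.049 for superiority in SAP 12.5.1.1. Amend SAP 10.0 to match, and state the sidedness of 0.001. If it is one-sided, reset the final level to about 0.048. Restating the global level as 5.1% is not a repair, because it conflicts with the one-sided 2.5% in SAP 12.0. The cost of 0.049 is about 0.5 mL of half-width and 0.2-0.3 points of power.
2. **Disclosure.** State in SAP 10.0 whether any interim changed N, and on which inputs. This costs a sentence or two. Only if the observed difference changed N, base the decision on a fixed-weight inverse-normal combination, or a conditional-error test, of stage-wise statistics from the planned ANOVA with predictive blood loss. Take the weights from the stage sizes in force before the change, and report a matching interval. This needs some programming, and the interval may widen or shift. If the log-transformed or van Elteren route is taken, the stage-wise statistics must follow it.
3. **Any re-estimation still to come.** Use only the SD, with the assumed difference held at 0.
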